2.3 Study Procedures and Schedule

2.3.1 Overview

Subjects with measurable unresectable pancreatic carcinoma will be enrolled in two groups. One group of subjects will have locally advanced, unresectable disease. The second group of subjects will have metastatic disease that is distant to the draining lymph nodes.

In this study, subjects will receive 3 mg/kg ipilimumab antibody intravenously every three weeks. Four doses will be designated as a course of therapy and evaluations will be conducted at the end of each course.

2.3.2 Screening Phase and Baseline

The Screening Phase was defined as the period prior to administration of study drug.

Baseline is defined as the last measurement before the first dose of study drug unless otherwise indicated.

2.3.3 Treatment Phase /Retreatment Cycle

Four doses will be designated as a course of therapy and evaluations will be conducted at the end of each course, three weeks after the 4th infusion. An informal interim evaluation may be performed three weeks after the 2nd infusion to rule out rapid disease progression, but the formal evaluation with tumor measurements will be performed approximately three weeks after the 4th dose. CT scanning may be performed at any time during protocol implementation in the event that there is clinical evidence of disease progression. A second course of treatment may be offered to subjects with progressive disease who tolerate the first course of treatment and are willing to undergo a second course of treatment with ipilimumab rather than pursue an alternate therapy at that time. Treatment will be limited to 2 courses of therapy. Subjects that respond (PR or CR) and subsequently relapse will be treated with up to 2 additional courses of therapy. Subjects may come off study at any time if rapid disease progression occurs. Subjects in the locally advanced disease group may experience sufficient

tumor response that their disease is rendered resectable. If this occurs, these subjects will be treated with standard pancreatic resection rendering them NED (no evidence of disease).

2.3.4 Follow-up Phase

Subjects will undergo physical examination, including vital signs, blood sampling for hematological, biochemical and HAHA evaluation and, as clinically indicated, chest radiography, pulmonary function, diagnostic imaging, three weeks following the last treatment, then at three month intervals for 1 year, at 6 month intervals for two years, and then at 12 month intervals or until disease progresses.

2.3.5 Study Completion/Early Withdrawal Visit

Prior to termination of participation in the study, each subject will undergo physical examination, diagnostic imaging, and blood sampling for hematological, biochemical, and immune function assessments.

2.3.6 Study Flow Chart

Table 2: Schedule of Assessments, Day 0 through Termination of Participation

Schedule	On-Study Evaluations					Follow-up Variable ^{1,8}
	2	3	4	5	6 ⁷	
Visit	2	3	4	5	6 ⁷	
Day	0	21 ±2d	42 ±2d	63 ±2d	84 ±2d	
MDX-010 Dose (mg/kg)	3	3	3	3	3	
Adverse events	X	X	X	X	X	X
████████████████████	X	X	X	X	X	X
Physical examination	X	X	X	X	X	X
Assessment for ocular symptoms	X	X	X	X	X	X
Vital signs ³	X	X	X	X	X	X
Performance Status	X	X	X	X	X	X
Ophthalmologic examination**					X	
Pulmonary Function Testing ²					X	X
Diagnostic imaging					X	X
Hematology		X	X	X	X	X
Biochemistry (including amylase and lipase)		X	X	X	X	X
Urinalysis					X	X
Pregnancy test ⁴	X	X	X	X	X	
ANA ⁵					X	
Antithyroglobulin					X	
Thyroid Function Test ⁶					X	
Blood (PBMC) sample					X	
PK sample ⁹	X			X		
HAHA sample ¹⁰	X				X	
Infusion of MDX-010	X	X	X	X	X	

Disease Response					X	X
1: 3-month intervals for 1 year, 6-month intervals for 2 years, and 12-month intervals until recurrence of disease. 2: PFT's will be performed if subjects develop any clinical sign or symptom suggestive of deterioration of pulmonary function.. 3: Vital signs will be monitored every 30 minutes for the duration of the ipilimumab infusion and for one hour following infusion completion, and then routinely unless otherwise indicated. 4: A negative pregnancy test will be confirmed prior to each dose of ipilimumab in women of childbearing potential; refer to section 2.2.7 C of the protocol. 5: If ANA positive, perform the EBA. If ENA positive, perform the tests indicated in Section 3.4.2.5 of the protocol. 6: If abnormal, run full thyroid panel, including Free T3 and Total T4. 7: A second course of 4 additional infusion ipilimumab (every 3 weeks x 4) may be given if the subject shows toxicities of grade 1 or less after the first course. 8: Up to 2 Subsequent courses of 4 infusions each ipilimumab (every 3 weeks x 4) may be given to subjects with complete or partial responses that have relapsed (PD). 9: For 5 subjects in each group, blood samples (5 mL) for the analysis of plasma concentrations of ipilimumab will be drawn prior to the 1 st and 4 th doses of ipilimumab and again at 1 hour post-infusion. 10: For 5 subjects in each group, blood samples (1 mL) for the analysis of HAHA will be drawn at baseline and 3 weeks after the last infusion of the subject's last course of treatment. **: Additional ophthalmologic exams will be performed if the subject experiences ocular symptoms						

3. Study Populations

3.1 Safety Population

Safety population includes all subjects in the study who received at least 1 dose or any partial dose of study medication.

4. Analysis Parameters

4.1 Safety Parameters

The safety parameters include treatment emergent adverse events (TEAE), immune related adverse events (irAE), clinical laboratory tests (hematology, biochemistry, urinalysis, pregnancy test, antinuclear antibody (ANA), autoimmune panel, antithyroglobulin, thyroid function tests, HAHA (5 subjects in each group), etc.), ophthalmologic examination, pulmonary function test, vital sign measurements, ECOG, and physical examinations, etc.

4.3 Other Parameters

Other parameters include ECG and chest X-ray.

5. Statistical Method

All data collected in this study will be analyzed by the Biostatistics group in Medarex, Inc. or its designees.

All data will be listed individually. For quantitative parameters, descriptive statistics will include the mean, standard deviation, minimum, median, and maximum. For qualitative parameters, descriptive statistics will include the frequency and percentage.

5.1 General Statistical Considerations

Unless otherwise indicated, the statistical significance will be declared if the two-sided p-value is ≤ 0.05 .

5.2 Protocol Violations

Any protocol violations that impact clinical activity were determined by the investigator and Medarex medical monitor.

5.3 Sample Size Determination

The primary objective of this study is to assess the clinical response of partial response (PR) or complete response (CR) to ipilimumab as a single agent in subjects with locally advanced pancreatic adenocarcinoma. This trial was conducted as a Phase II clinical trial using an optimal design [REDACTED]. The trial will seek to rule out an undesirably low response probability of 5% ($p_0=0.05$) in favor of a level which demonstrates potentially useful activity of 20% ($p_1=0.20$). With $\alpha=0.05$ and $\beta=0.10$. Initially 21 subjects will be enrolled. If ≤ 1 out of 21 subjects has an objective response (confirmed CR or PR), then accrual will stop and it will conclude that the treatment is not sufficiently active. If ≥ 2 out of 21 subjects demonstrate objective responses, then accrual will continue until 41 subjects have been enrolled. In the second stage, if 2-4 of 41 subjects respond, this will be insufficient activity to warrant further evaluation. If ≥ 5 of 41 subjects have documented objective responses, the treatment will be considered active in pancreatic carcinoma.

5.4 Disposition of Subjects

[figure not shown]
The frequency (number and percentage) of subjects in safety population will be presented. The frequency of reasons for discontinuation will also be presented.

5.5 Demographics and Baseline Characteristics

Subject demographics and baseline characteristics including age, sex, race, height, weight, time since diagnosis, cancer stages, medical history, prior therapies, prior surgeries, etc. will be summarized by group.

5.6 Study Drug Exposure

The MDX-010 total dosage (mg) and number of doses will be summarized by group using descriptive statistics.

5.8 Efficacy Analysis

Efficacy analysis will not be performed.

5.9 Safety Analysis

5.9.1 Adverse Events

All adverse events (AEs) and serious adverse events (SAEs) as documented by the investigator will be coded using the version 10.1 of Medical Dictionary for Regulatory Activities (MedDRA™).

Treatment-emergent adverse event (TEAE) is defined as an adverse event that emerges during treatment or within 70 days of the last dose of the study drug including the retreatment cycles, having been absent pre-treatment or worsens relative to the pre-treatment state. Any study drug related AEs will also be treated as TEAEs regardless of the start date. All adverse events regardless of being treatment emergent or not will be displayed in the AE listings. The treatment emergent AEs will be summarized using descriptive statistics. The non treatment emergent AEs will be listed separately.

An overview summary of subjects with any AE, any severe AE, any study drug related AE, any serious AE will be presented in a table. AEs will also be summarized in other tables as sorted by 1) system organ class and preferred term; 2) Grade 3 or above AEs by system organ class and preferred term; 3) Serious AEs by system organ class and preferred term; 4) system organ class, preferred term, and severity; 5) Serious AEs by system organ class, preferred term, and severity; 6) system organ class, preferred term, and relationship to study drugs; 7) system organ class, preferred term, severity and relationship to study drugs; and 8) Serious AE by system organ class, preferred term, severity and relationship to study drugs. In addition, the immune related AEs will be summarized by system organ class and preferred term.

5.9.2 Vital Signs

The observed vital signs (temperature, systolic and diastolic blood pressures, pulse rate, and respiration rate) at each visit and change from baseline to each post-baseline visit will be summarized by group using descriptive statistics.

5.9.3 Clinical Laboratory Tests

Clinical laboratory test values outside the normal range will be flagged in the data listing.

Laboratory data (hematology, biochemistry, urinalysis, pregnancy test, antinuclear antibody (ANA), autoimmune panel, antithyroglobulin, thyroid function tests, etc.) will be

summarized by group for scheduled visits based on individual visit values as well as change from baseline. Shift tables from baseline to post-baseline visits will also be presented.

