2.1.1 Inclusion Criteria

- A. Any patient ≥ 18 years of age with a histologic diagnosis of stage IV pancreatic adenocarcinoma that is clinically evaluable, with at least one site of measurable disease.
- B. Patients must be ≥ 3 weeks beyond their last treatment (radiation, chemotherapy, etc.) for pancreas carcinoma and recovered from any serious toxicity experienced during treatment.
- C. Women should be either: post-menopausal for at least one (1) year; surgically incapable of bearing children; or utilizing a reliable form of contraception. Women of childbearing potential must have a negative urine pregnancy test conducted during screening.
- D. Because the risk of a negative influence of this therapy on reproductive processes, men who may father a child must agree to the use of male contraception for the duration of their participation in the trial.
- E. Life expectancy ≥ 3 months.
- F. ECOG Performance Status ≤ 2 .
- G. Biliary obstruction must be effectively drained by endoscopic, operative or interventional means.
- H. Gastric outlet obstruction must be effectively drained by endoscopic, operative or interventional means.
- I. Required values for initial laboratory test:

- WBC $\geq 2500/\text{ml}$
- ANC $\geq 1500/\text{ml}$
- Platelets $\geq 100 \times 10^3/\text{ml}$
- Hemoglobin $\geq 9 \text{ g/dl}$
- Hematocrit $\geq 27 \%$
- Creatinine $< 2.0 \text{ mg/dl}$
- HBsAg negative
- HIV negative
- Anti-HCV non-reactive, or RNA-PCR (-) if reactive.

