5.3.1.6 Duration of stable disease

Stable disease is measured from the start of the treatment until the criteria for progression are met, taking as reference the smallest measurements recorded since the treatment started.

5.4 Toxicity Criteria:

Information about all adverse events, whether volunteered by the patient, discovered by investigator questioning, or detected through physical examination, laboratory test or other means, will be collected and recorded on the Adverse Event Case Report Form and followed, as appropriate. An adverse event is any undesirable sign, symptom or medical condition occurring after starting study treatment, even if the experience is not considered to be treatment-related.

Medical conditions/diseases present before starting study treatment are only considered adverse events if they worsen after starting study treatment. Clinical experiences occurring

before starting study treatment but after signing the informed consent form are recorded on the Medical History/Current Medical Conditions Case Report Form. Abnormal laboratory values or test results inducing clinical signs or symptoms are recorded on the Adverse Events Case Report Form under the signs, symptoms or diagnoses associated with them.

As far as possible, each adverse event will also be described by: its duration (start and end dates), the severity grade (Cancer Therapy Evaluation Program Common Toxicity Criteria, CTC AE 3.0, located on the internet at <http://ctep.cancer.gov/reporting/ctc.html>) and its relationship to treatment (unrelated/unlikely/possible/probable/definite), and the action(s) taken.

Serious adverse events

Information about all serious adverse events will be collected and recorded on the Serious Adverse Event Report Form. To ensure patient safety, each of such serious adverse events must also be reported to Medarex within 24 hours of learning of its occurrence.

A serious adverse event is defined in general as an untoward (unfavorable) experience which:

- Is fatal or life-threatening,
- Requires or prolongs hospitalization,
- Is significantly or permanently disabling or incapacitating,
- Constitutes a congenital anomaly or a birth defect,
- Jeopardizes the patient and may require medical or surgical intervention to prevent one of the outcomes listed above
- Is \geq grade 4 severity hematological adverse event
- Is \geq grade 3 severity non-hematological adverse event

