- Is \geq grade 3 severity infusion adverse event (occurring \leq 24 hours after start of infusion)

Events not considered to be serious adverse events are: hospitalizations occurring under the following circumstances--planned before entry into the clinical study, for elective treatment of a condition unrelated to the studied indication or its treatment, or part of the normal treatment or monitoring of the studied indication and not associated with any deterioration in condition; events occurring on an emergency, outpatient basis that do not result in admission (unless fulfilling the criteria above).

This study will utilize the CTC AE 3.0 for toxicity and adverse event reporting. A copy of the CTC AE 3.0 can be downloaded from the CTEP web site: <http://ctep.cancer.gov/reporting/ctc.html>. All appropriate treatment areas should have access to a copy of the CTC AE 3.0.

5.5 Statistical Section:

[figure not shown]
The primary objective of this study is to determine whether single agent MDX-010 antibody is able to result in clinical responses (PR or CR) in patients with stage IV pancreatic cancer. Our experience with MDX-010 in the melanoma and renal cell population has shown a correlation between autoimmune toxicity and tumor response.

For each of the two groups, this trial will be conducted as a Phase II clinical trial using an optimal design [REDACTED] The trial will seek

to rule out an undesirably low response probability of 5% ($p_0=0.05$) in favor of a level which demonstrates potentially useful activity of 20% ($p_1=0.20$). With an $\alpha=0.05$ (5% probability of accepting a poor combination, and $\beta=0.10$ (10% probability of rejecting a good combination), initially 21 patients will be enrolled. If 0-1 of 21 have a clinical response as defined in section 5.3, then accrual will stop and we will conclude that the combination is not sufficiently active in the disease being studied. If 2+/21 patients respond, then accrual will continue until 41 patients have been enrolled. If 2-4 of 41 respond, this will be insufficient activity to warrant further evaluation. If 5+/41 have documented clinical responses, the agent will be considered active in pancreatic carcinoma. Under this design if the null hypothesis were true (5% true response probability), there is a 72% probability of early termination.

It is expected that it will require 2-4 years to accrue up to 82 evaluable patients.

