6.1.2	Shift Table for Hematology (Safety Population)
6.2.1	Summary and Change from Baseline Biochemistry (Safety Population)
6.2.2	Shift Table for Biochemistry (Safety Population)
6.3.1	Summary and Change from Baseline Urinalysis (Safety Population)
6.3.2	Shift Table for Urinalysis - Part 1 (Safety Population)
6.3.3	Shift Table for Urinalysis - Part 2 (Safety Population)
6.4.1	Summary and Change from Baseline Thyroid Function Tests (Safety Population)
6.4.2	Shift Table for Thyroid Function Tests (Safety Population)
6.5	Shift Table for Autoimmune Panel Test (Safety Population)
7.1	Adverse Events Summary (Safety Population)
7.2	Adverse Events by System Organ Class and Preferred Term (Safety Population)
7.3	Grade 3 or Above Adverse Events by System Organ Class and Preferred Term (Safety Population)
7.4	Serious Adverse Events by System Organ Class and Preferred Term (Safety Population)
7.5	Adverse Events by System Organ Class, Preferred Term, and Severity (Safety Population)
7.6	Serious Adverse Events by System Organ Class, Preferred Term, and Severity (Safety Population)
7.7	Adverse Events Related to Study Drug by System Organ Class, Preferred Term (Safety Population)

Table #	Table Title
7.8	Adverse Events Related to Study Drug by System Organ Class, Preferred Term, and Severity (Safety Population)
7.9	Serious Adverse Events Related to Study Drug by System Organ Class, Preferred Term, and Severity (Safety Population)
7.10	Immune Related Adverse Event Summary (Safety Population)
7.11	Immune Related Adverse Events by System Organ Class, Preferred Term (Safety Population)

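### SAP 5.9.3 plans no CTC AE-graded or worst-value laboratory table and leaves the shift categories undefined, so asymptomatic or unscheduled grade 3-4 worsening may go uncounted

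*SAP*

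**What the plan says.** SAP 5.9.3 makes three separate statements about laboratory data.

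- Listing: "Clinical laboratory test values outside the normal range will be flagged in the data listing".
- Summaries: results will be "summarized by group for scheduled visits based on individual visit values as well as change from baseline".
- Shift tables: "Shift tables from baseline to post-baseline visits will also be presented". No category scale is given, and Tables 6.1.2 (hematology) and 6.2.2 (biochemistry) in SAP Appendix 1 are titles only.

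The grading scale is set in Protocol 5.4: "This study will utilize the CTC AE 3.0 for toxicity and adverse event reporting". The SAP tabulates grade and severity for adverse events only (SAP 5.9.1; Tables 7.3, 7.5, 7.6, 7.8 and 7.9).

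Entry (Protocol 2.1.1) allows hemoglobin down to 9 g/dl and creatinine just under 2.0 mg/dl. The listed laboratory requirements include no limit for bilirubin, ALT, AST or alkaline phosphatase, although the same section admits patients with prior obstruction: "Biliary obstruction must be effectively drained by endoscopic, operative or interventional means".

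**The concern.** SAP 5.8 drops the efficacy analysis, so the safety tables are the main output. A reader will want to know how many patients in each group developed severe hematology or biochemistry abnormalities, and whether these arose on treatment or were there at entry. In advanced pancreatic cancer with drained biliary obstruction, the second question is a live one, above all for liver tests.

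The planned laboratory tables are not specified to answer either question. The by-visit summaries give no count of patients by severity. The shift tables might, but their categories are not stated. Values from an unscheduled work-up, where a severe abnormality is often first seen or peaks, are outside the stated by-visit summary. If the adverse event tables do not pick these cases up, nothing graded will.

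**Working it through.** SAP 5.9.3 states no figure to reproduce. The check sets the passages side by side, with one calculation from the visit schedule.

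**1. Is there a graded laboratory table?** In SAP Appendix 1, Tables 6.1.1 to 6.5 are summaries, changes from baseline and shifts. None mentions a CTC AE grade, a worst post-baseline value or a count of grade 3-4 values. Grade appears only in the adverse event tables.

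**2. Do the adverse event tables close the gap?** Not reliably.
- Protocol 5.4 collects events found by any means, laboratory tests included. It then says: "Abnormal laboratory values or test results inducing clinical signs or symptoms are recorded on the Adverse Events Case Report Form", under the associated sign, symptom or diagnosis. An abnormal value without symptoms is not clearly covered.
- Protocol 7.4, the instructions for the adverse event form, leaves abnormal laboratory findings out of the definition.
- A site following 7.4 would not enter an asymptomatic grade 3-4 value. A site following the broad sentence in 5.4 might. Its presence in Table 7.3 therefore depends on which section was followed.

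**3. What does the scheduled-visit limit leave out?**
- During a course, blood is taken before each dose, every 21 days (Protocol 3.4.1 and schedule). Values between those visits are unscheduled.
- After the last dose, sampling is set at three weeks and then at three-month intervals (Protocol 3.7; SAP 2.3.4). The treatment-emergent window is 70 days (SAP 5.9.1).
- Taking three months as 13 weeks, the second draw falls on day 13 × 7 = 91 if counted from the last dose, or day 21 + 91 = 112 if counted from the three-week visit. Both are after day 70.
- The window thus holds one set laboratory visit, on day 21. Days 22 to 70 have none: 70 − 21 = 49 days, and 49/70 = 70% of the window.
- Two qualifications apply. A patient who starts another course is sampled before each dose. Blood is also taken before participation ends (Protocol 3.7; SAP 2.3.5), but that visit has no fixed day, and the SAP does not say whether it counts as scheduled.

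**4. What would one missed patient change?** If a group fills its first stage of 21 (SAP 5.3), one uncounted patient moves the group's grade 3-4 rate by 1/21 = 4.8 percentage points.

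**5. Why the shift scale matters (illustration only).** Suppose the shift tables used low/normal/high. A patient already out of range who worsens in the same direction stays in the same cell. Let q be the share of patients starting out of range in that direction, and RR their risk of grade 3-4 worsening relative to the others. The share of such worsenings showing no shift is q·RR / (q·RR + 1 − q).

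| q (assumed) | RR = 1 | RR = 2 |
|---|---|---|
| 25% | 25% | 0.50/1.25 = 40% |
| 50% | 50% | 1.00/1.50 = 67% |
| 75% | 75% | 1.50/1.75 = 86% |

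Neither q nor RR is in the documents, and the category scale is itself an assumption. The table shows why the scale must be stated. It does not estimate what the SAP would miss.

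**The case against.** The strongest reply is that much of the worsening remains visible.

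- The normal-range sentence governs flags in the listing, not the shift tables. A reader might infer low/normal/high shift tables, in which an abnormal starter who worsens shows no shift. The documents do not say so; the categories are simply undefined. This stands.
- The words limiting summaries to scheduled visits attach to the visit values and changes from baseline. The shift sentence refers to post-baseline visits without that limit, so whether unscheduled values enter the shift tables is open. This also stands.
- Descriptive statistics include the minimum and maximum (SAP 5). A hemoglobin fall from 9.5 to 6.5 g/dl at a scheduled visit enters as −3.0 and, if it is the largest fall, is printed as the minimum. Change from baseline does separate entry abnormality from later worsening for such values. But an extreme shows one patient at one visit and gives neither a count nor a grade.
- All data are listed individually, and events recorded as adverse events reach the graded tables whatever the visit. Events that worsen from the pre-treatment state count as treatment-emergent (SAP 5.9.1). This helps, but listings give no rate by group, and the adverse event route has the conflict shown above.
- The study is uncontrolled and terminated, and no stopping or efficacy conclusion depends on these tables. This limits the importance of the point but does not remove it.

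**Conclusion.** The point holds as a gap in specification with a cheap remedy. SAP 5.9.3 limits its by-visit laboratory summaries to scheduled visits, leaves the shift categories undefined, and plans no CTC AE-graded or worst post-baseline table. With abnormal values allowed at entry and Protocol 5.4 and 7.4 in conflict, asymptomatic or unscheduled grade 3-4 worsening may appear in no graded table.

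The only size that follows from the documents is the coverage gap: 49 of 70 post-dose days after the single set laboratory visit, for a patient who does not continue treatment and whose end-of-participation sample falls outside those days. A reader might go further and conclude that severe laboratory toxicity is understated, or by how much. The documents do not support that. They give no share of patients abnormal at entry, no rate of severe worsening and no duration of peaks, and several planned outputs capture part of what occurs. Understatement is a risk here, not a demonstrated result.

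**What to change.** In SAP 5.9.3 and the shells for Tables 6.1.2 and 6.2.2:

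- Tabulate baseline CTC AE 3.0 grade against worst post-baseline grade, by group, for the tests that CTC AE 3.0 grades, with low and high directions separate.
- Use all scheduled and unscheduled values from first dose to 70 days after the last dose, matching the treatment-emergent window.
- Add the number and percentage of patients with new or worsened grade 3-4 values.
- Keep the by-visit values and changes from baseline as supportive summaries.

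Reconcile Protocol 5.4 and 7.4 on whether laboratory findings are adverse events, and state in the SAP which rule governed the recorded data, so that Table 7.3 can be read correctly.

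The cost is SAP wording and a little more programming on data already collected. The downside is that worst-value rates will look less favourable and will include disease-related changes such as biliary re-obstruction. A footnote should say so.

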2.2.11 Thyroid function test

Thyroid stimulating hormone (TSH) – if abnormal, run full Thyroid function test (TFT panel, including Free T3 and Total T4).

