3.4.1.5. Assessment of adverse events

3.4.1.6. Assessment of concomitant medications

3.4.2 Assessment prior to each new course

3.4.2.1. Physical examination

3.4.2.2. Assessment of performance status

3.4.2.3. Diagnostic imaging appropriate to tumor evaluation, using the same imaging modality, method of assessment, or technique used for baseline evaluation. Repeat diagnostic imaging will be performed after each course of therapy (approximately day 55).

3.4.2.4. Ophthalmologic examination at the completion of course 1 and again if any ocular symptoms develop, including retinal pigmentation changes. Visual acuity will be performed during each assessment.

3.4.2.5. Autoimmune Panel:

Antithyroglobulin antibody

ANA, if positive perform the ENA, if ENA positive, perform the following tests (If negative, then a sample of serum will be stored for subsequent testing in the event that the ANA becomes positive at a later date):

- Anti-phospholipid antibody
- Anti-neutrophil cytoplasm antibody
- CH50
- Anti-DNA antibody
- Anti-SSA antibody
- Anti-SSB antibody
- Rheumatoid factor (RF)

3.4.2.6. Thyroid function tests, as defined for baseline in Section 2.2.12.

3.4.2.7. Hematology (Hemoglobin, Hematocrit, Complete blood cell count with differential and platelet count (direct) and sedimentation rate, and biochemistry testing (Albumin, Alkaline phosphatase, ALT, AST, Bilirubin (total and direct), Calcium Chloride, Bicarbonate, Creatinine, Glucose, Lactate dehydrogenase (LDH), Potassium, Sodium, Total protein, Urea nitrogen (BUN), Uric acid)

3.4.2.8. Pulmonary function tests will be conducted if patients develop any clinical sign or symptom suggestive of deterioration of pulmonary function.

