Medarex reserves the right to discontinue any study for administrative reasons at any time. If appropriate, reimbursement for reasonable expenses will be made. Authorized physicians must notify ORKAND when a patient is taken off study.

3.7 Post Study Evaluation (Follow up):

Patients will undergo physical examination, including vital signs, blood sampling for hematological and biochemical evaluation and, as clinically indicated, chest radiography, pulmonary function, diagnostic imaging, three weeks following the last treatment, then at three month intervals for 1 year, at 6 month intervals for two years, and then at 12 month intervals or until disease progresses. Prior to termination of participation in the study, each patient will undergo physical examination, diagnostic imaging, and blood sampling for hematological, biochemical, and immune function assessments.

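### SAP 5.9.3 ties the thyroid and autoimmune tables to scheduled visits, and the first course schedules these tests once (Day 84), so early stoppers and off-schedule abnormal results can be missing

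*SAP*

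**What the plan says.** **Analysis.** SAP 5.9.3 names ANA, the autoimmune panel, antithyroglobulin and thyroid tests among the laboratory data, which are to be "summarized by group for scheduled visits based on individual visit values as well as change from baseline". It then adds: "Shift tables from baseline to post-baseline visits will also be presented". SAP Appendix 1 turns this into Table 6.4.1 (thyroid, values and change), Table 6.4.2 (thyroid, shift) and Table 6.5 (autoimmune panel, shift only), all in the Safety Population.

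**Timing.** The schedules in Protocol 3.4 and SAP 2.3.6 mark ANA, antithyroglobulin and thyroid tests at Day 84 and leave the follow-up column blank. Protocol 3.4.2 repeats them before each new course. The visit three weeks after the last treatment (Protocol 3.7, SAP 2.3.4) names hematology and biochemistry, to which the SAP adds HAHA. It names neither thyroid nor autoimmune tests. Before a patient leaves the study, Protocol 3.7 and SAP 2.3.5 call for "blood sampling for hematological, biochemical, and immune function assessments", without defining the last item.

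**Testing rules.** TSH is measured in everyone (Protocol 2.2.11); "if abnormal, run full Thyroid function test (TFT panel, including Free T3 and Total T4". ANA and antithyroglobulin are also done in everyone. The rest of the panel is stepwise (Protocol 3.4.2.5): "ANA, if positive perform the ENA, if ENA positive, perform the following tests". Protocol 2.2.10 and 3.4.2.5 store serum for later testing should the ANA turn positive.

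**The concern.** Protocol 3.1 and 5.5 link autoimmune toxicity to this antibody, and the SAP has dropped efficacy, so these tables are part of what the study will now report. If a table draws only on a visit 12 weeks after the first dose, it describes patients who were still being assessed at that point.

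Those who leave sooner are unlikely to be a random subset. Protocol 3.3.1 ends dosing for systemic steroid use, for autoimmune toxicity that does not resolve, and for symptomatic uveitis. Protocol 3.6 allows removal for progression. The toxicity being measured can therefore decide who is measured. A thyroid or autoantibody test ordered because a patient became ill, or drawn at withdrawal, has no slot in a summary by scheduled visit. Without a stated denominator, a reader could take a low count of new abnormalities as reassuring when some patients were never tested after baseline.

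**Working it through.** The documents attach no figure to this point, so the check sets the schedule against the analysis rule.

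**Step 1. Which visits carry the tests.** Doses in the first course fall on Days 0, 21, 42 and 63 (SAP Table 1). The post-treatment visit comes 21 days after the last dose.

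| Last dose given | Visit 3 weeks later | Thyroid, ANA and antithyroglobulin scheduled then? |
|---|---|---|
| Day 0 | 0 + 21 = Day 21 | No |
| Day 21 | 21 + 21 = Day 42 | No |
| Day 42 | 42 + 21 = Day 63 | No |
| Day 63 | 63 + 21 = Day 84 | Yes |

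Only a patient who receives all four infusions has that visit coincide with the scheduled tests (ignoring dose delays). Patients off drug are still followed until they meet off-study criteria, so some may be sampled near Day 84. Nothing in the schedules requires it.

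**Step 2. How far the rule reaches.** The scheduled-visit limit is explicit for visit values and change from baseline, hence for Table 6.4.1. The shift sentence speaks of post-baseline visits and gives no rule for unscheduled or withdrawal samples. For Tables 6.4.2 and 6.5, exclusion is therefore the natural reading in context, not a stated rule. The SAP's only missing-data rule (section 6.1) concerns adverse-event onset dates.

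**Step 3. Illustration of scale.** Take one group of 21, the first-stage size. Let *e* be the fraction with no Day 84 sample (assumed; not in the documents). Baseline-to-Day-84 pairs = 21 × (1 − *e*); patients without a pair = 21 × *e*.

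| *e* | Pairs | No pair |
|---|---|---|
| 20% | 16.8 | 4.2 |
| 40% | 12.6 | 8.4 |
| 60% | 8.4 | 12.6 |

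**Step 4. Second-line tests.** Assume *e* = 20%, 5% to 20% first-line abnormal at baseline, 80% of those still abnormal at Day 84, and 15% new first-line abnormality among the rest. All of these rates are assumed.

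- Pairs on a test triggered directly by the first-line result, such as Free T3: 16.8 × 0.05 × 0.8 = 0.7, up to 16.8 × 0.20 × 0.8 = 2.7.
- New second-line results with no baseline: 16.8 × 0.80 × 0.15 = 2.0, up to 16.8 × 0.95 × 0.15 = 2.4.

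The same 2.0 to 2.4 patients still appear as normal-to-abnormal on the first-line test, because it was done at both times. For ENA and the ENA-triggered tests, stored serum can also supply the missing baseline. The protocol states no such use for thyroid, although section 3.4.2.9 stores serum at baseline in general.

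**The case against.** **Other output exists.** SAP section 5 lists every result individually, and 5.9.3 flags laboratory values outside the normal range. SAP 5.9.5 separately promises a descriptive summary of the autoimmune panel and thyroid tests with no scheduled-visit limit. Symptomatic events reach the immune-related adverse-event tables (7.10 and 7.11). This stands in part. Listings preserve the data but give no rate or denominator, and Appendix 1 names no thyroid or autoimmune table other than 6.4.1, 6.4.2 and 6.5. Protocol 7.4 excludes a laboratory finding alone from its adverse-event definition, so the event tables are not a full backstop.

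**The tests are not confined to Day 84.** They recur before each new course, and the withdrawal visit includes some immune testing. The first part is correct, but later courses go to patients who came through the first with toxicity of grade 1 or less, not to early stoppers. The second is undefined and does not name thyroid.

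**Only table titles are given.** Nothing says a patient without a value is dropped rather than shown as missing. That is fair, and it is why the conclusion is that patients can be absent, not that they will be.

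A reader might also infer that the stepwise testing removes new-onset cases from these tables. The documents do not support that. The first-line tests are unconditional. A patient with abnormal TSH but normal Free T3 and Total T4 at entry has a baseline for both, so a later change in either is a valid shift.

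**Conclusion.** The point holds for timing and denominators. Under the scheduled-visit rule, patients who stop before Day 84 and abnormal results from for-cause or withdrawal samples can be missing from Tables 6.4.1, 6.4.2 and 6.5, and the loss can be related to the toxicity being measured. The likely direction is understatement of new abnormalities. The second-line gap is a smaller matter of display.

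The size is unknown. A reader might take the entry requirement of at least 3 months' life expectancy and compute deaths before Day 84 from exponential survival, 1 − 0.5^((84/30.4)/*m*). That gives 47% for a median *m* of 3 months and 27% for 6 months. The documents support neither the medians nor the survival shape, and an eligibility floor is not a median, so these figures are not an estimate for this trial. The fractions in the working likewise only show scale.

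The analysis is descriptive, so no error rate, sample size or decision rule is affected. This is a cheap improvement to a safety-only report, and it goes beyond missing detail because the stated rule itself leaves out early and unscheduled results.

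**What to change.** In SAP 5.9.3 and Tables 6.4.1 to 6.5:

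1. Base the change and shift tables on TSH, ANA and antithyroglobulin, with change from baseline only where the result is quantitative.
2. Show shifts to the worst and to the last post-baseline value, using all post-baseline results, including unscheduled and withdrawal samples.
3. Count every safety subject, with a *no post-baseline sample* category. For second-line tests, add *not tested – first-line normal/negative*.
4. Where stored serum was tested, treat the result as baseline according to its collection date.

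The cost is table shells and programming. The downside is that some shifts will come from off-schedule days, and for-cause samples are more likely to be abnormal, so both should be labelled in the tables.

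If patients were still being followed, the three first-line assays could be added to blood already drawn at the post-last-dose or termination visit. SAP 5.10 shows that the trial had been terminated when the plan was written, so the table change is the part that can be acted on.
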